1.5.3 Adverse neurodevelopment and routine fortification

When added to human milk, current fortifiers provide about 1.1-2.4g additional protein/100 ml in an appropriate ratio with non-protein energy. Preterm milk protein in the first month averages around 1.5g/100 ml but the range is wide (0.7-2.4 g/100 ml) Given that total feed volumes of 180-200 ml/kg are common in the UK, routine fortification risks providing very high protein intakes, exceeding 5g/kg/day, which may be damaging to neurodevelopment (8). Concerns have been raised that accelerated weight gain from fortification increases the risks of adverse long-term consequences such as obesity, insulin resistance and hypertension (4). The findings of a systematic review and meta-analysis of planned high protein intake after birth for infants born preterm was that this might be harmful for survival, neurodevelopment and metabolism during infancy, and does not improve growth after the neonatal period. The authors concluded that protein intakes ≥ 3.5 g/kg/d should not be recommended for children born preterm (8).

We performed an analysis of 5 years of whole population data from the UK National Neonatal Research Database (NNRD) in which we compared very preterm infants who had received fortified human milk feeds and those that had not (35,389 infants) (unpublished data). We employed Targeted Maximum Likelihood Estimation, a machine learning approach to address confounding in observational data and maximise causal inferences. We found infants receiving fortified feeds had substantially higher "survival to 34 weeks gestational age without surgical NEC" (Risk Difference 15.1%, 95% CI 14.5 to 15.7). The risk difference increased with decreasing gestational age. "Surgical NEC" was also lower in infants receiving fortified feeds but with a smaller effect size (Risk

Title: COLLABORATE	EDGE No: 181495	Sponsor: Imperial College London	Version: 3.0; 09/01/2026
---------------------------	---------------------------	--	---------------------------------

Difference -1.4%, 95% CI -1.7 to -1.1). These data may reflect residual confounding but also provide justification for a randomised trial.

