5.3 Randomisation: timing and method

5.3.1 Timing

Babies may participate in either or both randomisations; see Flow Chart, Appendix 1.

Randomisation 1 to pHDM or Preterm Formula, will occur when the attending clinician decides a supplemental feed is required because the volume of Own Mother's Milk is insufficient.

Randomisation 2, to routine fortification or no routine fortification, will occur when the baby is receiving between 60-120 ml/kg/day of human milk feeds (Own Mother's Milk and/or pHDM). By "fortification" we mean immediate or incremental increase to "full strength fortification" according to neonatal unit practice. We refer to "no routine fortification" because rescue fortification is permitted (see section 5.6.2).

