7 STATISTICAL ANALYSES

7.1 Statistical Analysis Plan

We will construct a detailed Statistical Analysis Plan, signed off by the Chief Investigators and Trial Steering Committee prior to the first interim analysis. We will summarise baseline characteristics by randomisation arm within each comparison using appropriate statistical measures (mean, standard deviation; median, interquartile range; frequencies; percentages). The flow of participants through both comparisons will be reported according to the CONSORT Extension for Adaptive Designs (32). We will target a treatment policy estimand to estimate the effect of each intervention as delivered in practice regardless of any events that occur post-randomisation. The efficacy and safety analyses for both randomisations will be based on the intention-to-treat population. Missing data is expected to be very low as this is retrieved from NNRD. It is specified in the Parent Information Leaflet that should they withdraw consent for their baby's participation, data already available in the NNRD will be utilised.

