7.3 Primary endpoint analysis

We will model the main intervention effect for each randomisation separately. For both, we will use a binomial Generalized Estimating Equation (GEE) model with identity link and a log link function to estimate adjusted risk difference and adjusted risk ratio (in line with CONSORT reporting recommendations) with robust variance. This will enable us to account for within network correlations. Intervention effect for the first and second randomisation will be modelled separately. Both models will be adjusted for minimisation variables.

The analysis model for randomisation 1 will include whether or not an infant received fortification (Y/N) and whether or not they were randomised to this (randomisation 2; Y/N)). Though randomisation 2 will occur after randomisation 1, they are close in time and receiving fortification may be more likely to be a predictor of the primary outcome than a result of taking part in randomisation 1. Therefore, randomisation 2 and receipt of fortification will be treated as baseline covariates.

The analysis model for randomisation 2 will include adjustment for taking part in randomisation 1 (Y/N) and type of supplementary feed received (pHDM or formula). A supplementary analysis for randomisation 2 will be performed to determine the effect of rescue fortification in the standard of care arm (no routine fortification) will be undertake using principal stratum and complier average causal effect approaches (no rescue fortification is defined as a complier in the standard of care arm). In the unlikely case that missing data are greater than 2%, a sensitivity analysis will be performed using multiple imputation.

Title: COLLABORATE	EDGE No: 181495	Sponsor: Imperial College London	Version: 3.0; 09/01/2026
---------------------------	---------------------------	--	---------------------------------

Binary secondary and key safety outcomes (death, surgical NEC, medical NEC, infection) will be analysed using the same principled approach as the primary outcome. The age 2-year PARCA-R will also be evaluated as a continuous outcome and the between arm mean difference estimated using the GEE model with normal distribution and identity link function adjusting for minimisation variables.

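### The randomisation 1 primary model adjusts for two post-randomisation variables (fortification received, entry to randomisation 2) as if they were baseline, which departs from the treatment policy estimand and can bias the arm effect

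*Protocol*

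**What the plan says.** Section 7.3 specifies the randomisation 1 model: "The analysis model for randomisation 1 will include whether or not an infant received fortification (Y/N") and also whether the infant took part in randomisation 2. It concedes the order of events: "Though randomisation 2 will occur after randomisation 1, they are close in time". Its reason for including the variables anyway is that "receiving fortification may be more likely to be a predictor of the primary outcome than a result of taking part in randomisation 1". It concludes: "Therefore, randomisation 2 and receipt of fortification will be treated as baseline covariates".

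Four other places bear on this:

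- Section 7.1 sets the target: "We will target a treatment policy estimand to estimate the effect of each intervention as delivered in practice", whatever happens after randomisation.
- Section 5.3.1 says randomisation 2 "will occur when the baby is receiving between 60-120 ml/kg/day of human milk feeds", and counts both own mother's milk and donor milk (pHDM) as human milk.
- Section 1.2 describes fortifier as a powder added to human milk, again meaning own mother's milk and pHDM.
- Section 5.6.2 allows later rescue fortification for faltering growth in randomisation 2 babies, which also makes a baby fortified.

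For randomisation 2, section 7.3 adjusts for "type of supplementary feed received (pHDM or formula").

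**The concern.** A covariate can be treated as baseline only if the allocation could not have changed it. Here it could. A baby allocated pHDM builds up human milk volume from the supplement and a baby allocated formula does not, so the arm can affect who reaches randomisation 2, when, and how much feed there is to fortify. Fortification also requires survival and feed tolerance. A baby who dies or has surgical NEC first is coded unfortified, so the covariate partly records the outcome.

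Where both links exist, comparing arms within fortified and unfortified babies no longer compares randomised groups. A null effect could be reported as harm from one feed, or a real benefit could be masked, in the primary comparison of a trial meant to be definitive. That fortification predicts the outcome strongly is no defence for a post-randomisation variable, because a stronger association makes the distortion larger.

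**Working it through.** **1. The plan's own figure.** Section 7.2.1 states at least 87% power with 1084 per arm, 0.82 v 0.87, 2% missing and looks at 50%, 75% and 100%.

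- Analysed per arm: 1084 x 0.98 = 1062.
- SE = sqrt((0.82 x 0.18 + 0.87 x 0.13)/1062) = 0.0157.
- Standardised effect = 0.05/0.0157 = 3.19.

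With the section 7.4 boundaries (2.863, 2.337, 2.024), group-sequential power is 88.3% with pooled variance and 88.5% with unpooled variance, and overall alpha is 0.0498. The stated power is reproduced. It makes no use of the two covariates, so removing them does not change it.

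**2. When the adjustment biases a null effect.** Let q be the failure probability before fortification could start, and r = (0.18 - q)/(1 - q) the failure probability afterwards, both equal in the two arms. Let p1 and p0 be the shares fortified (pHDM, formula) among babies who reach that stage, so the shares fortified overall are F1 = (1 - q)p1 and F0 = (1 - q)p0. Regress event-free survival on arm and fortification with an identity link:

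- fortification coefficient g = (0.18 - r)(F1 + F0) / [F1(1 - F1) + F0(1 - F0)]
- adjusted arm effect under the null = -g x (F1 - F0)

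The bias is zero if F1 = F0 (no dependence on arm) or if g = 0 (no dependence on survival or frailty). It needs both.

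**3. Size.** The 18% failure rate is 1 - 0.82 (section 7.2.1). The n of 1908 is the randomisation 1 row of the section 7.4 table. The protocol gives no fortification rates by arm and no timing of failures, so p1, p0 and q are assumptions. Rejection is for a single look at two-sided 5% with a robust SE.

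| p1/p0 | q | F1 / F0 | g | Adjusted RD (points) | SE (points) | Rejection |
|---|---|---|---|---|---|---|
| 50/50 | 0.03-0.09 | equal | 0.05-0.15 | 0.0 | 1.7-1.8 | 5% |
| 55/45 | 0.03 | 0.534 / 0.437 | 0.050 | -0.5 | 1.77 | 6% |
| 55/45 | 0.06 | 0.517 / 0.423 | 0.100 | -0.9 | 1.76 | 8% |
| 55/45 | 0.09 | 0.501 / 0.410 | 0.150 | -1.4 | 1.74 | 12% |
| 60/40 | 0.03 | 0.582 / 0.388 | 0.051 | -1.0 | 1.80 | 9% |
| 60/40 | 0.06 | 0.564 / 0.376 | 0.102 | -1.9 | 1.79 | 19% |
| 60/40 | 0.09 | 0.546 / 0.364 | 0.154 | -2.8 | 1.77 | 35% |

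Worked line (60/40, q = 0.06): r = 0.12/0.94 = 0.1277. Then g = 0.0523 x 0.940/(0.2459 + 0.2346) = 0.102, and the bias is -0.102 x 0.188 = -0.019. A negative sign means against pHDM, and follows from assuming more fortification in that arm.

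**4. Comparison of scale.** Section 1.5.3 reports an observational association between fortified feeds and event-free survival of "Risk Difference 15.1%, 95% CI 14.5 to 15.7". Used only as a possible value of g, it gives shifts of 0.151 x 0.05 = 0.8, 0.151 x 0.10 = 1.5 and 0.151 x 0.20 = 3.0 points for arm differences in fortification of 5, 10 and 20 points.

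**5. Without the covariates.** A separate large-sample simulation, with both covariates in the adjusted model, compared it with the model without them. The latter recovered the true risk difference to within about 0.2 points in every scenario, for true differences of 0 and 5 points.

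**The case against.** The strongest defence is that the imbalance may be small. The planned numbers imply that 2 x 2168 - 3252 = 1084 babies, half of each randomisation, are in both. Among these, routine fortification is allocated at random and does not depend on the randomisation 1 arm. If they split 50/50 in each arm, with similar entry by arm and no rescue, an overall 60/40 needs 70/30 among the rest, and 55/45 needs 60/40. Formula-arm babies also take human milk: maternal intention to express is an inclusion criterion, and section 1.4 says the shortfall is often temporary. If the two randomisations really are close in time, few failures may fall between them. The illustration also omits the minimisation variables and randomisation 2 participation. Adding participation, with half co-enrolled, lowers the 60/40 rejection rates to 8%, 18% and 32%.

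All of this limits the size. None of it makes the variables baseline, because unequal entry to randomisation 2 by arm is exactly what the entry rule permits.

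A reader might infer more than the documents support:

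- **That the primary estimate is certainly biased.** It is not if either dependence is absent under the null.
- **That section 1.5.3 demonstrates the mechanism**, through 15.1 points in event-free survival against 1.4 in surgical NEC. That is observational, in a wider very preterm population, without event timing, and the protocol itself allows for residual confounding.
- **That the interim decisions inherit the bias.** Section 7.4 calls the differences unadjusted in one sentence and adjusted in the next, so this is open.
- **That randomisation 2 loses power because never-supplemented babies have no feed type.** Nothing says they are dropped.

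**Conclusion.** Wrong as written. The model conditions on variables that follow randomisation 1, that the protocol's feeding rules tie to the arm, and that require survival. It therefore does not estimate the stated treatment policy effect. The justification offered, closeness in time and being more a predictor than a result, does not answer this.

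Bias under a true null is conditional on fortification differing by arm and also depending on survival or frailty. On the assumptions in the working it runs from zero at 50/50 to -2.8 points at 60/40, against a target difference of 5 points, with single-look rejection of 5% to 35%. These figures show scale and are not predictions; neither size nor direction can be settled from the documents. If the interim Z-scores come from the adjusted model, the same bias can reach the stopping decisions.

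The randomisation 2 model has a related but lesser weakness. Section 5.3.1 lets a baby reach the required volume on own mother's milk alone and need a supplement later, so the type of feed received may be determined after randomisation 2.

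**What to change.** - Delete receipt of fortification and randomisation 2 participation from the randomisation 1 primary model and from any interim model based on it. Adjust only for the minimisation variables and, if wanted, other variables fixed before randomisation 1.
- Move any fortification-adjusted or joint-effect analysis to a supplementary analysis.
- In the randomisation 2 model, replace the type of supplementary feed received with randomisation 1 status at the moment of randomisation 2: not randomised, pHDM or formula. Every baby then has a value fixed before that allocation.
- In section 7.4, say whether the interim differences are adjusted and for which variables.

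The cost is protocol and SAP wording. No extra babies or data are needed, and the stated power stands because it never relied on these covariates.

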5.2 Consent

5.2.1 Type and timing of consent

5.2.1.1 Main study

As this study compares interventions that are already in widespread use, verbal consent will be sought for the main study. This will be documented in the eCRF and medical/research records by the member of the clinical care team who has explained the study and sought consent. Verbal consent is well received by parents and clinicians and has been used in other RCT evaluating interventions that are already in wide use, including the current NIHR funded clinical trial of a medicinal product, BASE (ISRCTN 18260410).

The verbal consent statement will be completed by the participating site staff electronically in OpenClinica to aid central monitoring of consent data. A paper back-up version may be used where access to the OpenClinica database is not possible.

Participants will be provided with a copy of the Participant Information Sheet and completed verbal consent statement. Consent will be sought a time considered clinically appropriate and before the baby has received any supplemental feeds or fortifier.

Before discharge from the neonatal unit, a discussion will take place with parents to remind them that the trial team will contact them at 2 years to ask them to complete the Parent Report of Children's Abilities-Revised (PARCA-R) questionnaire. At discharge, parents will be asked to confirm their contact details are up to date to improve data return rates.

Title: COLLABORATE	EDGE No: 181495	Sponsor: Imperial College London	Version: 3.0; 09/01/2026
---------------------------	---------------------------	--	---------------------------------

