5.7 Follow-up

No research-related follow-up visits are required. Age 2-year cognitive and language outcomes will be obtained using the parent-completed PARCA-R in accordance with NICE recommendation (30). A digital version of the PARCA-R will be made available to clinical teams should they wish to use this in which case parents will be registered to do so at neonatal unit discharge (31).

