7.2 Sample size and power

7.2.1 Main study

This is a group-sequential trial with 2 interim and 1 final analysis (i.e., an adaptive trial), hence the sample size is not fixed. The maximum sample size is 3252, (n=2168 in each randomisation; n=1084 per arm) assuming no early stopping, estimated on the composite primary efficacy outcome (survival to 34 weeks gestational age without surgical NEC (Y/N)).

Title: COLLABORATE	EDGE No: 181495	Sponsor: Imperial College London	Version: 3.0; 09/01/2026
---------------------------	---------------------------	--	---------------------------------

For the randomisation 1 (pHDM vs Formula supplement) an observational analysis of NNRD data estimated the difference in the proportion surviving to 34w PMA for babies born <29 weeks' gestation to vary between 0.18 and 0.52 depending on week of gestational age (favouring supplementation with preterm formula) (6) For the sample size calculation we targeted a highly conservative MCID in this proportion of 0.05 based on a baseline of 0.82 which we accurately estimated from the NNRD for this population of babies in the UK (i.e. from 0.82 to 0.87).

For randomisation, 2 (fortifier vs no routine fortifier) an unpublished observational analysis from NNRD data estimated the difference in proportion data surviving to 34w PMA for babies born <29 weeks gestation to vary between 0.06 and 0.75 depending on week of gestational age (favouring fortifier). Taking a conservative approach and in line with the first comparison, we have chosen to target the same MCID of 0.05.

We have calculated power based on a fixed sample size of 3252 unique babies using rpact (33) where interim timings were chosen to minimise the expected sample size. We anticipate at least 50% of babies will be co-enrolled into both randomisations. If co-enrolment is higher, power will increase. We have used an O'Brien & Fleming design with two-sided overall significance level of 5% to account for two interims at 50% and 75% and a normal approximation assumption for rates. For both randomisations we have factored in 2% missing outcome data due to carers withdrawing consent from routine data collection in NNRD.

Based on all the above assumptions, n=3252 (n=2168 in each randomisation and n= 1084 per arm) will achieve a minimum of 87% power for each randomisation. The expected sample size across for each randomisation is n=2439.

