7.4 Interim assessment of efficacy

We will conduct two pre-planned formal interim efficacy analyses when 50% and 75% of participants reach 34 weeks gestational age (i.e., primary outcome is available). This analysis will be undertaken by an independent ICTU statistician. Recruitment will continue during interim analyses. The analysis will employ two-sided O'Brien-Fleming efficacy boundaries. Unadjusted between arm differences in proportions will be calculated using the primary analysis models described for the final analysis. An identify link function will be used to obtain adjusted risk differences and corresponding Z-scores. Superiority will be assessed at each stage based on the critical value thresholds (Z-scores) and numbers of participants.

Proportion recruited	50%	75%	100%
Randomisation 1, n	954	1431	1908
Randomisation 2, n	1063	1594	2126
Critical value thresholds (Z-scale)	2.863	2.337	2.024

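### The 2% missing-data rule suits NNRD outcomes but is not limited to them; applied to the two-year composite, which needs a returned PARCA-R, it over-weights death

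*Protocol*

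**What the plan says.** Section 7.1 gives the general premise, without exception: "Missing data is expected to be very low as this is retrieved from NNRD". Section 7.2.1 allows for 2% missing outcomes and attributes them to withdrawal of consent for NNRD data. Section 7.3 gives the rule: "In the unlikely case that missing data are greater than 2%, a sensitivity analysis will be performed using multiple imputation". Later in 7.3, binary secondary and key safety outcomes are sent through the approach used for the primary outcome. The PARCA-R is also to be analysed as a continuous score, which implies that a binary analysis is planned too.

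The two-year endpoints in section 2.4.2 include the binary composite of survival without moderate-severe cognitive-language impairment. Its impairment part is not routine NNRD data. Section 5.7 takes it from the PARCA-R, which parents complete. Section 5.2.1.1 says the trial team will contact parents at two years, and adds: "At discharge, parents will be asked to confirm their contact details are up to date to improve data return rates". Under section 5.2.2.1, PARCA-R results enter the NNRD record with parental consent, so the NNRD receives these data but does not guarantee them. The protocol gives no expected return rate and no separate rule for missing questionnaires.

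**The concern.** The composite is observed in two unequal ways. A death before discharge is recorded in the NNRD and settles the composite as a failure without a questionnaire. A survivor can be scored only if a parent replies. If imputation is only a sensitivity analysis, the main model runs on the babies whose composite is known: all recorded deaths, plus only those survivors whose parents replied. Non-return therefore depends on part of the outcome itself, and the estimate is biased even if replies are completely random among survivors.

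At stake is a secondary endpoint with some weight. Language and cognition at two years are the named secondary objective (section 2.2), the composite carries the value hypothesis for randomisation 2 (section 1.3.3), and better two-year cognitive-language outcomes trigger the decision model in section 7.9.

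**Working it through.** **The plan's own figure.** Section 7.2.1 has "n=2168 in each randomisation; n=1084 per arm", rates 0.82 and 0.87, 2% missing, O'Brien-Fleming looks at 50%, 75% and 100%, and at least 87% power.
- Per arm after 2% loss: 1084 × 0.98 = 1062.
- Pooled standard error: √(2 × 0.845 × 0.155 / 1062) = 0.0157, so the drift is 0.05 / 0.0157 = 3.18.
- With critical values 2.863, 2.337 and 2.024, simulation gives two-sided alpha 0.0499 and power 88.3%.

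This agrees with the stated minimum. The 2% allowance does its job for the primary outcome.

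**Inputs for the composite.**
- Death d: about 10% to discharge (section 6.8).
- Impairment in survivors i: not given for this population; 25% assumed. The trial cited in section 1.5.2 had 16.2% and 27.2%.
- Non-return in survivors q: not given; 10% to 40% shown, at random among survivors.

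**Formulas** (unadjusted).
- True success = (1 − d)(1 − i).
- Available-data success = (1 − d)(1 − q)(1 − i) / [(1 − d)(1 − q) + d].

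**When is the 2% limit met?** Missing share = (1 − d)q = 0.9q. This is at most 0.02 only if q ≤ 0.022, so about 98% of survivors' parents must reply. At 20% and 40% non-return, 18% and 36% of composites are missing.

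**One arm, d = 0.10, i = 0.25.** True success = 0.90 × 0.75 = 67.5%. At q = 0.2: 0.54 / 0.82 = 65.9%. At q = 0.4: 0.405 / 0.64 = 63.3%. The share of deaths in the analysed set rises from 10% to 0.10 / 0.82 = 12.2% and 0.10 / 0.64 = 15.6%.

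**Difference between arms, in points** (second arm minus first; deaths 11.5% v 8.5%).

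| Impairment | True | q = 10% | q = 20% | q = 30% | q = 40% |
|---|---|---|---|---|---|
| 25% v 25% | +2.25 | +2.45 | +2.68 | +2.96 | +3.30 |
| 25% v 28% | −0.50 | −0.27 | −0.01 | +0.31 | +0.70 |

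In the second row at 40% non-return, the bias is 0.70 + 0.50 = 1.2 points (1.19 before rounding). About 1062 × 0.64 = 680 babies per arm are analysed, so the standard error is √(2 × 0.62 × 0.38 / 680) = 2.6 points and the bias is about 0.45 of it.

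**A wider gap in deaths.** With deaths 12% v 8% and impairment 20% v 25%, the true difference of −1.40 becomes −0.70 at 20% non-return and +0.32 at 40%. The bias at 40% is 1.72 points, about 0.7 of a standard error of 2.6.

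**A large effect does not change sign.** With deaths 12% v 8% and impairment 16.2% v 27.2%, the true −6.8 becomes −4.7 at 40% non-return.

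**The case against.** The strongest reply is that the rule's reach is inferred. The 2% sentence stands in the section on the primary endpoint, before secondary outcomes are mentioned. The list that follows the reference to binary secondary outcomes names death, surgical NEC, medical NEC and infection, none of which uses the PARCA-R. The protocol never writes complete-case or available-data. A detailed analysis plan is promised, and realistic questionnaire loss would exceed 2% and so trigger imputation anyway. Steps to support return are also described: a reminder before discharge, contact-detail checks and a digital form.

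Part of this stands. The available-data main analysis is a reading of 7.1 and 7.3 together, not a stated choice. However, the 7.1 premise has no exception, imputation is given only a sensitivity role, and triggering it leaves the biased estimate as the main result. A later analysis plan that corrected this would have to depart from the protocol's text.

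A reader might also infer that the plan is likely to reverse the trial's conclusion on cognition. The documents do not support that. For randomisation 1, the evidence in section 1.5.2 points the same way on both counts: more impairment and lower survival without NEC surgery with pHDM. For randomisation 2, opposition appears only if the observational 15.1-point difference, which section 1.5.3 says may reflect residual confounding, is set against a concern about high protein intake; the review cited there suggests possible harm to survival as well. In the −0.50 example, the full-data standard error is about 2.0 points, so chance alone would give the wrong sign about 40% of the time. Section 2.4.2 also lists survival and impairment separately, so opposing components would be visible.

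**Conclusion.** The point holds as a mismatch between a missing-data rule built for NNRD outcomes and a secondary endpoint that depends on a parent questionnaire. Following the rule as written over-weights death in the two-year composite: about 1.6 points too low within an arm at 20% non-return and 4.2 points at 40%, given 10% deaths and 25% impairment.

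The bias in the between-arm difference is modest: just under 1.2 points in the example with a three-point gap in deaths, and larger if the gap is wider. A change of sign needs opposing effects on death and impairment that nearly cancel, and return well short of complete. The over-weighting of death needs neither.

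The result rests on assumed impairment and return rates, on non-return at random among survivors, and on deaths to discharge only; deaths after discharge are not covered by these figures. The primary outcome and its 2% allowance are not affected.

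**What to change.** - In 7.1 and 7.3, limit the expectation of very low missing data, and the 2% sensitivity-only rule, to NNRD-derived outcomes.
- For the two-year composite and its impairment component, make the main analysis one that restores non-returning survivors. One option is multiple imputation of impairment, by arm, among babies not known to have died, using NNRD predictors such as gestation, growth centile, surgical NEC, severe brain injury and bronchopulmonary dysplasia. The other is inverse-probability-of-return weighting applied to survivors only.
- Keep the available-data result as a sensitivity analysis.
- State the expected PARCA-R return.

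The cost is a change of wording and modest programming, with predictors already in the NNRD and no new data collection. The main analysis would then rely on data being missing at random given those predictors. That is a real assumption, but weaker than what the available-data composite needs, since deaths are never missing for want of a questionnaire.
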